### 6.2.2 Phone follow-up - Visit 2 (Day 7 $\pm$ 1)

- All concomitant medications being taken by the patient will be checked and, in case of changes from the baseline/treatment visit, will be recorded in the patient's medical records and in the appropriate section of the eCRF;
- The occurrence of general and specific adverse events from the previous visit will be checked and (if any) will be recorded in the patient's medical records and in the appropriate section of the eCRF; Visit 2 (phone follow-up visit) will represent the conclusion of patient's participation in the study.

## 7. SAFETY

Complete and accurate data on all adverse events (AEs) experienced for the duration of the study reporting period will be reported on an ongoing basis in the AE forms of the eCRF.

It is important that each AE report includes a description of the event, its expectedness, whether it is considered serious, its duration (onset and resolution dates), its intensity, its relationship to the medical device, any other potential causality factors, any action taken and its outcome.

Note: After completion of the investigation, the Sponsor will continue to have an obligation to report serious and treatment-related AEs affecting the investigation subjects.

Refer to Section 7.1.4 for procedures of reporting of serious adverse events (SAEs), devices deficiencies (DD) and medical device incidences.

### 7.1 Medical Device – Class I

#### 7.1.1 Definition of (Serious) Adverse Events and other safety related events

An Adverse Event (AE) is defined as “any untoward medical occurrence, unintended disease or injury, or untoward clinical sign (including abnormal laboratory findings) in subjects, users or other persons, whether related to the investigational medical device”.

This definition is restricted to events related to the investigational medical device and includes: events related to the investigational medical device, events related to the study procedures and events related to the device users or to other persons involved.

An **Adverse Device Effect (ADE)** is defined as an AE related to the use of the medical device.

This definition includes any AEs resulting from insufficiencies or inadequacies in the instructions for use, in the deployment, the implantation, the installation, the operation, or any malfunction of the medical device. It also includes any AE resulting from a user error or from the intentional abnormal use (misuse) of the investigational medical device. All ADEs will be classified as Serious/Non-Serious according to the categories of seriousness and as Mild, Moderate or Severe according to the intensity classification. In addition, the investigator will always be asked to express his/her judgment about the causality relationship with the medical device.

**Device deficiencies (DDs)** are defined as any inadequacy of the medical device with respect to its identity, quality, durability, reliability, safety or performance, including malfunctions, use errors, and inadequate labelling. A malfunction is defined as a failure of the investigational medical device performance compared to its intended purpose, when used in accordance with the instructions for use or protocol. All DDs will be documented during the clinical investigation and reported to the Sponsor on the appropriate form.

A device deficiency not leading to an AE but that could be the cause of a medical occurrence if suitable actions have not been taken, if intervention had not been made, or if circumstances had been less fortunate, must be reported in the same way of an adverse event.

A **Serious Adverse Event (SAE)** is any untoward medical occurrence or effect that:

- Results in death;
- Is life-threatening;

- Requires inpatient hospitalisation or prolongation of existing hospitalisation;
- Results in persistent or significant disability or incapacity;
- Is a congenital anomaly or birth defect;
- Is an important medical event (i.e. important medical reactions that jeopardize the patient or may require intervention to prevent one of the other outcomes listed in the above definition).

The term “life-threatening” in the definition refers to an event in which the subject was at risk of death at the time of the event; on the contrary, it does not refer to an event which hypothetically might have caused death if it was more severe.

In addition, important medical events that may not be immediately life-threatening or result in death, or require hospitalisation, but that may jeopardise the patient or may require a medical intervention to prevent one of the other outcomes listed above, should also be considered serious. (ICH E2A).

SAEs should be followed up until resolution or stabilisation. Participants with ongoing SAEs at the moment of their study termination (including safety visit) will be further followed up until recovery or until stabilisation after the study termination.

Any adverse event which does not fall into the above-described categories is to be defined as Non-Serious.

Seriousness must not be confused with the intensity of the event (severity).

Planned hospitalization for a pre-existing condition, or a procedure required by protocol, without serious deterioration in health, is not considered a SAE, but part of the medical history.

Causal Relationship of SAE [MEDDEV 2.7/3 revision 3, May 2015]:

A causal relationship towards the medical device or study procedure should be rated as follows:

- **Not related:** The relationship to the device or procedures can be excluded.
- **Unlikely:** The relationship with the use of the device seems not relevant and/or the event can be reasonably explained by another cause, but additional information may be obtained.
- **Possible:** The relationship with the use of the investigational device is weak but cannot be ruled out completely. Alternative causes are also possible.
- **Probable:** The relationship with the use of the investigational device seems relevant and/or the event cannot reasonably be explained by another cause.
- **Causal relationship:** The serious event is associated with the investigational device or with procedures beyond reasonable doubt.

Device deficiencies that might have led to an SAE are always related to the medical device.

**Serious Adverse Device Effect (SADE)** is an ADE that has resulted in any of the consequences characteristic of a SAE. All SADEs will be recorded in this study.

An **Unanticipated Serious Adverse Device Effect (USADE)** is defined as a SADE which by its nature, incidence, severity, or outcome is not identified in the current version of the risk analysis report.

An **Anticipated Serious Adverse Device Effect (ASADE)** is an effect which by its nature,

incidence, severity or outcome has been identified in the current version of the risk analysis report.

**A Device Deficiency with SAE potential** is a device deficiency that might lead to a serious adverse event if a) suitable actions have not been taken or b) interventions have not been made or c) if circumstances have been less fortunate.

Health hazards that require measures: Findings in the trial that may affect the safety of study participants, and which require preventive or corrective measures intended to protect the health and safety of study participants.

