## 7.2 Method of Recording and Assessing Adverse Events

It is responsibility of the Investigator to collect all AEs (both serious and non-serious) derived by spontaneous, unsolicited reports of subjects, by observation and by routine open questionings (e.g., how have you felt since I saw you last? is there anything new that you wish to discuss?).

All Adverse Events occurring during the clinical investigation (starting from the signature of the informed consent and until the end of the study) must be documented in the patient's medical records and in the Adverse Event forms on the eCRF, irrespectively of their classification; the Adverse Event forms should be completed in English, possibly writing clearly in capital letters. If the eCRF system is not available, the paper SAE reporting form will be filled in (in English language, written in clear capital letters) and reported according to the indications provided in section 7.1.4.

For any adverse event, the following information will be recorded: description of the event, date of onset and date of end, intensity, correlation with investigational product, action taken and outcome.

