### 7.2.4 Reporting of (Serious) Adverse Events and other safety related events

All SAEs/SADEs and DDs that could have led to a serious adverse device effect must be reported, whether or not considered causally related to the medical device, or to the study procedure(s). All the above-mentioned events will be recorded in the eCRF no later than 24 hours after acknowledging the occurrence of the event. If the eCRF system is not available, the paper SAE/DD/Device Incidents reporting form will be filled in (in English language, written in clear capital letters) and must be sent via email to the Sponsor at the email address indicated below.

Day 0 is the day the Investigator becomes aware of an event occurred to the subject, and it is used by the Sponsor as reference day for regulatory purposes. Each SAE and SADE must be tracked and assessed by the Sponsor. The Sponsor will report any SAEs/SADEs to the relevant Independent Ethics Committee (IEC) as required by local requirements of the committee and to the Competent Authority. The Sponsor will determine whether a SADE is considered “anticipated” or not. Each DD must be tracked and assessed by the Sponsor. Any DD that might have led to a SAE if suitable action had not been taken or intervention had not been made or if circumstances had been less fortunate will be reported to the Competent Authority.

All SAE/DD/Device Incidents, independently of their causal relationship, must be reported immediately (within 24 hours) in the eCRF SAE form; if the eCRF system is not available, the paper reporting form must be reported immediately (within 24 hours from awareness) via email or Certified Electronic Mail by the Investigator or his delegated to:

[name], Endostart s.r.l., [name].

[contact]

Certified Electronic Mail: [[contact]](mailto:[contact])

Email: [[contact]](mailto:[contact]) and [[contact]](mailto:[contact])

Initial notification should include:

- Identification of the Principal Investigator: name, address, study center, telephone number;
- Study protocol number;
- Subject's identification (ID number in the study, date of birth, sex, relevant medical history);
- Device name or code, beginning and end of treatment;
- Description of event and its onset;
- Measures undertaken to treat it;
- Opinion of the Investigator about the relation of the event to the tested medical device.

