### 8.2 Determination of Sample Size

Efficacy (first primary objective) will be assessed by measuring the colonoscopy completion rate in long-lasting procedures, which is a measurable parameter of clinical value recognized by international medical societies. Safety (second primary objective) will be assessed by measuring the rare of adverse events. They are classified into: serious gastrointestinal events; myocardial infarction; stroke; pneumonia. Based on the literature [30]; their occurrence rates in screening or surveillance colonoscopy are 47 persons, 4 persons, 7 persons and 10 persons per 100'000, respectively.

These two objectives are merged in one indicator, which is equal to 1 for each subject if the procedure is incomplete or an adverse event occurs, and 0 otherwise.

The non-completion rate of long-lasting colonoscopies conducted with Endorail is expected to be around 10%. This will be compared to the above-mentioned threshold of 20% for incomplete procedures. It should be noted that this threshold is conservative and represents the most critical setting for comparison with respect to the state of the art, as it is derived from the lower bound of the range from the literature.

When including the safety to provide the expected value of the indicator for Endorail and the corresponding threshold, the above values of 10% minimally change, as the adverse event

occurrence rate is 0.068% (given by the sum of the occurrence of the 4 events reported above per 100'000 persons, expressed in percentage).

With a significance level  $\alpha$  of 5%, assuming a proportion of outcome of 10.1%, 85 patients allow to test with a power of 80% the  $H_0: p \geq 20\%$  vs  $H_1: p < 20\%$ , where 20% is the estimated percentage of incomplete procedure from literature.

The chosen number is then increased by the 10% to account for possible drop-out (e.g., cases to be discarded, losses to follow-up, etc.), resulting in  $85/0.90 = 95$  patients to be actually enrolled.

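### The adverse event definition in Section 7.1.1 contradicts itself and the rules to record all events; if its restriction is applied, unrelated non-serious events go uncounted, in the device's favour

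*Combined protocol and SAP*

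**What the plan says.** Section 7.1.1 of the combined protocol and SAP defines an AE in two steps. The first sentence covers any untoward occurrence "in subjects, users or other persons, whether related to the investigational medical device"; the words *or not* are missing after *whether*. The second sentence narrows this: "This definition is restricted to events related to the investigational medical device and includes: events related to the investigational medical device". Its list then continues with "events related to the study procedures and events related to the device users or to other persons involved".

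Other sections ask for every event:

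- Section 7, opening: "Complete and accurate data on all adverse events (AEs) experienced for the duration of the study reporting period will be reported".
- Section 7.2: "All Adverse Events occurring during the clinical investigation (starting from the signature of the informed consent and until the end of the study) must be" entered in the medical records and on the AE forms, however they are classified.
- Section 8.4: AEs are presented regardless of their relation to the device.
- Section 7.2.4: serious events "must be reported, whether or not considered causally related to the medical device". The definition of a serious event in 7.1.1 has no relatedness limit, and the causality scale there includes a category for no relation.

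These events feed primary quantities. Under Section 3.1 and the Synopsis, one primary safety endpoint compares AE rates with colonoscopies done without Endorail, and another is the absence of device-related serious events. Section 8.2 adds a composite indicator, "equal to 1 for each subject if the procedure is incomplete or an adverse event occurs, and 0 otherwise". Section 8.1 describes the same composite with serious adverse events only.

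**The concern.** A definition decides what counts as an AE before any rule about recording AEs comes into play. Sections 7, 7.2 and 8.4 all use the term that 7.1.1 defines. A site could therefore state truthfully that it recorded all AEs and still have left out an event it judged to be related to neither the device, the procedure nor a user.

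That judgement is made by an investigator who knows the device was used, in an open-label single-arm trial (Section 4.1). One element of the filter, relation to the device, cannot be applied at all to colonoscopies done without it. A filtered trial count set against such colonoscopies would not be like-for-like, and the error would run in favour of Endorail. If the composite counts any AE, the same omission would also lower the rate tested against 20%.

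**Working it through.** **Step 1. Which events can be lost.** Setting the rules side by side for a study patient:

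| Event | Restricting sentence in 7.1.1 | Other rules | Outcome |
|---|---|---|---|
| Related to the device or a study procedure | An AE | Recorded | Captured |
| Serious, related to none of the listed sources | Not an AE | Own definition in 7.1.1 has no relatedness limit; 7.2.4 requires a report | Captured |
| Non-serious, related to none of the listed sources | Not an AE | 7, 7.2 and 8.4 want it, but through the defined term | Lost if the restriction is applied |

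Only the last row is exposed.

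**Step 2. The plan's own figures (Section 8.2).**

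- Reference rate: (47 + 4 + 7 + 10)/100,000 = 68/100,000 = 0.068%, as stated. Added to 10% it gives 10.068%, which the plan carries as 10.1%.
- Sample size, one-sided α = 5%, power 80%, p0 = 0.20, p1 = 0.101, normal approximation:

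  n = [(1.645·√(0.20·0.80) + 0.842·√(0.101·0.899)) / (0.20 − 0.101)]² = 84.8, so 85, as stated.
- Drop-out: 85/0.90 = 94.4, so 95, as stated.

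**Step 3. Success rule of the planned exact one-sided binomial test.** The rule is the largest c with P(X ≤ c | n, 0.20) ≤ 0.05.

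- n = 95: c = 12, actual level 4.2%.
- n = 85: c = 10, actual level 3.3%.

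These are for a single final test; the two interim looks are not included.

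**Step 4. If the composite counts serious events only (Section 8.1).** Take the extreme case in which every event in the reference rate is dropped.

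- Expected number of such events in 95 patients: 95 × 0.00068 = 0.065.
- Exact power with p1 = 10.000% against 10.068%: 84.8% against 84.2% at n = 95, and 77.2% against 76.6% at n = 85.
- Chance of false success at a true rate of 20% with 0.068 points uncounted, n = 95: 4.4% instead of 4.2%.

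**Step 5. If the composite counts any AE (Section 8.2).** Let m be the share of patients whose only qualifying event is a non-serious, unrelated AE that goes unrecorded. The documents give no value for m, so 1, 2 and 5 percentage points are assumptions. With a true composite rate of 20%, the chance of false success is P(X ≤ c | n, 0.20 − m).

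| m | Patients uncounted, of 95 | n = 95, c = 12 | n = 85, c = 10 |
|---|---|---|---|
| 0 | 0 | 4.2% | 3.3% |
| 1 point | 0.95 | 6.8% | 5.3% |
| 2 points | 1.9 | 10.6% | 8.3% |
| 5 points | 4.75 | 31.7% | 25.3% |

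**The case against.** The strongest reply is that the text as a whole points to collecting everything. Section 7.1.1 defines an adverse device effect separately, which would be largely redundant if every AE already had to be device-related. Section 7 treats relation to the device as an item on each AE report. Sections 7.2 and 8.4 expect unrelated events. Colonoscopy with Endorail is itself a scheduled study procedure, so bleeding, perforation, petechiae or pain attributed to it stay within the list, and Sections 6.2.1 and 6.2.2 have these specific events checked at both contacts. All of this stands. It makes the bias conditional on someone following the restricting sentence. It does not remove the contradiction, since for non-serious events the other rules depend on the term being restricted.

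The reply also disposes of several stronger readings that a reader might infer:

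- *Only device-related events count.* The list also takes in events related to study procedures, users and other persons.
- *Infarction, stroke and pneumonia would be lost, (4 + 7 + 10)/68 = 31% of the reference rate.* Where serious, these are captured by the serious-event definition and Section 7.2.4. They amount to 95 × 21/100,000 = 0.02 expected events.
- *The reference rates count events of any cause.* Sections 1.2.4 and 8.2 give occurrence rates with no attribution rule.
- *Trial rates are lower by construction.* They are lower only if the restriction is applied.
- *An assumed 5% AE rate among completers moves the indicator from 10.1% to 0.101 + 0.899 × 0.05 = 14.6%.* That figure measures the conflict between serious AEs (8.1) and any AE (8.2). The restriction would remove only the unrelated part of that 5%.

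**Conclusion.** Wrong as written. Section 7.1.1 contradicts its own opening sentence and the rules in Sections 7, 7.2 and 8.4. The exposure is confined to non-serious events related to none of the listed sources. Serious events are largely protected, and the endpoint on the absence of device-related serious events is unaffected, because it is device-related by design.

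For the AE-rate comparison the direction is clear, favouring the device, but the size cannot be calculated: the documents give no reference rate for non-serious events. For the composite, the effect is negligible under Section 8.1, about 0.6 points of power even if the whole reference rate vanished. Under Section 8.2 it could be material, with false success rising from 4.2% to between 6.8% and 31.7%. That range rests on the assumed 1 to 5 uncounted points, a true composite rate of 20%, 95 analysed patients, a single final test, and sites actually applying the restriction.

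**What to change.** In Section 7.1.1, insert *or not* after *whether* in the first sentence and delete the restricting sentence for study patients. If a restriction is wanted to keep reports on users and other persons manageable, confine it to them. Keep relatedness as a recorded attribute of each event, not a condition for recording it. Section 7.1.1 then agrees with Sections 7, 7.2, 7.2.4 and 8.4.

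The cost is a small text change, a note to sites and a few more AE forms. Events never recorded may not be recoverable at analysis, so the change belongs before data collection, or as early in it as possible. Whether the composite counts serious or any AEs (8.1 against 8.2) is a separate matter, but it should be settled at the same time because it decides how much this point weighs.

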## 7.2 Method of Recording and Assessing Adverse Events

It is responsibility of the Investigator to collect all AEs (both serious and non-serious) derived by spontaneous, unsolicited reports of subjects, by observation and by routine open questionings (e.g., how have you felt since I saw you last? is there anything new that you wish to discuss?).

All Adverse Events occurring during the clinical investigation (starting from the signature of the informed consent and until the end of the study) must be documented in the patient's medical records and in the Adverse Event forms on the eCRF, irrespectively of their classification; the Adverse Event forms should be completed in English, possibly writing clearly in capital letters. If the eCRF system is not available, the paper SAE reporting form will be filled in (in English language, written in clear capital letters) and reported according to the indications provided in section 7.1.4.

For any adverse event, the following information will be recorded: description of the event, date of onset and date of end, intensity, correlation with investigational product, action taken and outcome.

### 7.2.1 Intensity of an adverse event

Each Adverse Event will be rated on a 3-points scale of increasing intensity:

- **Mild:** The event causes a minor discomfort, or does not interfere with daily activity of the patient, or does not lead to either modification of investigational product dosage or establishment of a correcting treatment;
- **Moderate:** The event perturbs the usual activity of the patient and is of a sufficient severity to make the subject uncomfortable. Subject is able to continue in study and local or non-invasive treatment for symptoms may be needed;
- **Severe:** The event prevents any usual routine activity of the patient and causes severe discomfort. It may be of such severity to cause the definitive interruption of treatment.

### 7.2.2 Outcome

Each Adverse Event will be rated by choosing among:

- Recovered/resolved;
- Recovered with sequelae;
- Not recovered;
- Recovering;
- Fatal;
- Unknown.

### 7.2.3 Medical Device Incidents

According to MEDDEV 2.12-1, Rev. 8, a medical device incident is defined as ‘any malfunction or deterioration in the characteristics and/or clinical performance of a device, as well as any inadequacy in the labelling or the instructions for use, which, directly or indirectly, might lead to or might have led to the death of a patient, or USER or of other persons or to a serious deterioration in their state of health’. A medical device incident that would require reporting includes:

- a) Serious public health threat: any event type which results in imminent risk of death, serious deterioration in state of health, or serious illness that requires prompt remedial action (MEDDEV 2.12-1 rev.8);
- b) Death or UNANTICIPATED serious deterioration in state of health of a subject that resulted in:
  - 1) A life-threatening illness or injury, or
  - 2) A permanent impairment of a body structure or a body function, or
  - 3) In-patient or prolonged hospitalization, or
  - 4) Medical or surgical intervention to prevent life-threatening illness or injury or permanent impairment to a body structure or a body function;
- c) Other events: events that have an established link between the device and the event.

